- i. **Secondary Hot Spots:** Theoretically speaking, there is a potential risk due to secondary hot spots that may occur along the beam path outside the focus. This has been reported in the literature for different types of transducer configurations using similar frequencies. The ExAblate system, with its unique, highly focused transducer configuration, was tested extensively using advanced simulations. The results of this work showed no evidence of significant hot spots away from the focal area. In any case, the real time thermal imaging feedback samples the entire field of view around the targeted tumor. These thermal images are displayed during the course of the energy delivery and therefore if any evidence of a secondary hot spot is observed, the treating physician will be able to utilize the ExAblate system “real-time” stop sonication button that instantaneously halts energy delivery. Importantly, the system is well equipped to handle it in real time and prior to incurring any tissue damage by shutting down the sonication prior to use of a Stop Sonication button being depressed..
10. **Neurological risks** Thermal “lesioning” in the brain may lead to heat transfer to immediately surrounding brain tissue or to hemorrhage. For a short period of time following the treatment, the surrounding tissue may be affected by inflammatory reaction. The length of the period cannot be predicted, but would be expected to resolve in 2-3 weeks based on our prior experience with sequential imaging in focused ultrasound thalamotomy for ET. These mechanisms may cause transient local neurological deficits or symptoms. These complications are not typically permanent. If these symptoms are detected, medical management with dexamethasone and/or mannitol might be effective. In severe cases, a craniotomy can be performed to relieve increased intracranial pressure, and permanent neurological deficits or death could possibly result.

No benefit – The subject may receive no benefit from this procedure. While ablation of the Vim has generally been shown to be effective in tremor reduction, there is the chance that it will not be effective for the subject, or that the effect may not be permanent.

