1.4.2.1.2.3 Study for Essential Tremor - Outside the United States

In addition to the Swissmedic study that included cohort of 1 subject (study is still on-going) with Essential tremor, InSightec conducted separate studies for the treatment of Essential tremor in both Canada and in Korea. A total of 8 subjects were treated to date as follows: 3 subjects in Canada, and 5 subjects in Korea. Both of these study protocol were similar to the FDA feasibility study (IDE G#100169). Overall, the ExAblate treatment safety profile is no different from the FDA feasibility study (for more details, see Section-1.4.2.1.2.4) nor from the safety profile of typical thalamotomy device procedures such as RF ablation and DBS. In short, safety events such as Dizziness and vomiting were reported, and both resolved without sequelae.

1.4.2.1.2.4 ExAblate Transcranial System Feasibility Study for Essential Tremor IDE - G100169

InSightec received FDA approval for a feasibility study of ExAblate Transcranial System for unilateral thalamotomy in the treatment of Essential Tremor under IDE # G100169. Fifteen subjects were enrolled and treated at one site and the study report was recently completed. Both the safety and effectiveness profiles showed a very favorable outcome of the ExAblate Transcranial MRgFUS treatment of patients with medication-refractory movement disorders, namely ET. The clinical outcomes subscales as well as the quality of life measures showed a substantial improvement in subject disabilities and their quality of life.

The incidence (number of patients experiencing an event) and severity of all device and procedure related AEs are summarized in Table 2. This list of events includes the non-significant and the significant anticipated treatment side effects as well as the events incidental to the treatment.

Table 2 Overall Adverse Events and Severity: ET-001

| | Event | Mild | Moderate | Severe | Total # of Events |
|------------------------------------|-------------------------|------|----------|--------|-------------------|
| Non-Significant Anticipated Events | Ache – pin site | 1 | 0 | 0 | 1 |
| | Balance | 7 | 0 | 0 | 7 |
| | Chest Pain | 1 | 0 | 0 | 1 |
| | Neural Deficit - speech | 2 | 0 | 0 | 2 |

Table 2 Overall Adverse Events and Severity: ET-001

| | Event | Mild | Moderate | Severe | Total # of Events |
|--|--------------------------------|-----------|-----------|----------|-------------------|
| | Neural Deficit – hand strength | 1 | 0 | 0 | 1 |

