| | Emesis | 2 | 0 | 0 | 2 |
| | Fatigue | 3 | 0 | 0 | 3 |
| | Headache 1 Day | 4 | 5 | 0 | 9 |
| | Headache > 1 Day | 1 | 2 | 0 | 3 |
| | Numbness -- appendage | 1 | 0 | 0 | 1 |
| | Nausea | 2 | 4 | 0 | 6 |
| | Paresthesia - appendage | 3 | 0 | 0 | 3 |
| | Paresthesia - face | 4 | 1 | 0 | 5 |
| | light headedness | 7 | 1 | 0 | 8 |
| | Twitch | 1 | 0 | 0 | 1 |
| | Warm Sensation | 4 | 0 | 0 | 4 |
| | Edema | 1 | 0 | 0 | 1 |
| | Ataxia | | 1 | 0 | 1 |
| Non-Significant Subtotal | | 45 | 14 | 0 | 59 |
| Significant Treatment Anticipated Events | Balance | 2 | 2 | 0 | 4 |
| | Fatigue | 1 | 0 | 0 | 1 |
| | Infection – pin site | 1 | 0 | 0 | 1 |
| | Numbness – pin site | 1 | 0 | 0 | 1 |
| | Parasthesia - appendage | 1 | 1 | 0 | 2 |
| | Parasthesia - face | 4 | 1 | 0 | 5 |
| | Parasthesia - scalp | 4 | 0 | 0 | 4 |
| | Hypesthesia - scalp | 1 | 0 | 0 | 1 |
| | Burn – pin site | 1 | 1 | 0 | 2 |
| | Significant Subtotal | 16 | 5 | 0 | 21 |

Table 2 Overall Adverse Events and Severity: ET-001

| | Event | Mild | Moderate | Severe | Total # of Events |
|-------------------|----------------------------|-----------|-----------|----------|-------------------|
| Incidental Events | Sinusitus | 0 | 1 | 0 | 1 |
| | Bronchitus | 1 | 0 | 0 | 1 |
| | Incidental Subtotal | 1 | 1 | 0 | 2 |
| | Total | 62 | 20 | 0 | 82 |

The most significant results shown in Table 2 are that all these events are indeed anticipated events and were already identified as potential events in the study protocol. Furthermore, NONE of the adverse events reported to date were severe in nature. In fact, 76 % (62/82) were Mild events, and the remainder 24% (20/82) were Moderate. Most of these events resolved either the same day (49% of the total events) or within 2 weeks of treatment (26% of the total events). Hence, 61 events (i.e. 74%) resolved within 2 weeks of the procedure.

Of all the events that did not resolve within the first 2 weeks post procedure, 14 out of 82 events (17%) resolved in more than 2 weeks (not counting the incidental sinusitis (n=1)), and 7 events (9%) were reported as ongoing.

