6 RISK ANALYSIS

Worldwide, over 8000 treatments have been performed to date with the MR guided FUS ExAblate body system. Risk analysis for InSightec ExAblate systems/clinical investigations has been conducted as part of previously approved FDA IDE submissions (G930140, G990151, G990184, G990201, G000203, G010225, G020001, G020182, G050177, and G060023, G070022, G080009, G080206, G100127, G100169, P040003 and subsequent supplements, and P110039). This data has been re-examined by the study sponsor and it has been concluded that this risk analysis has limited applicability to the proposed clinical investigation. The key consideration here is the fact that this proposed study is conducted with an ExAblate transcranial system that is completely different from the body system. This system is referred to internally as the Brain system. However, in principle, the body and brain systems have the same purpose namely to coagulate soft tissue within the body by means of MR guided high intensity focused ultrasound. Additional risks, new and unique to this study are presented in **Section-6.2**.

The potential risks described below will be explained to the subject in the informed consent process.

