1. Pain and/or discomfort – There is a risk of discomfort to the subject caused by heating of tissue. Focused ultrasound therapy involves precisely controlled pulses of thermal energy resulting in tissue coagulation (typically 55-65°C for several seconds) in small tissue volumes. This induces thermal coagulation of the targeted soft tissue. The energy intensity at the level of the skin away from the pin sites is quite low and sonication through scar tissue should be avoided.. The subject may experience both a cold sensation from the active cooling circulation of water within the rubber diaphragm as well as a rise in temperature in the skull which should be kept to below pain level by the active cooling. Because the focal point of the beam will be > 2.5 cm from the dura and there are no pain receptors in the brain, there should be no pain associated with ablation, itself.

The subject will be in constant verbal contact with the neurosurgeon and appropriate action can be taken in the event that a subject does experience pain discomfort. Remedies could involve lowering energy levels, or increasing the time interval between consecutive treatment pulses. The subject also has the ability to abort the sonication at any time by activating a handheld cut off circuit (i.e., stop sonication button).

See also Risk 9c regarding heating of the dura mater and the meninges.

2. Headache – The subject may experience a headache during or after the procedure which may be related to the pin site, slight swelling around the ablated brain tissue, or a reaction to the contrast media and should be transient.
3. Disorientation, light-headedness, dizziness, unsteadiness, nausea/vomiting: There is a potential risk that the subject will have sensations of light-headedness, dizziness, unsteadiness or even nausea/vomiting. Based on the current data, these events should be transient and resolve within a day or so.
4. Occurrences of transient numbness, tingling, eye twitch, hyperesthesia and/or paresthesia of the scalp, face and upper extremity have been reported in subjects undergoing Vim ablation for essential tremor. These generally are transient and resolved within minutes to one day. One paresthesia lasted for 4 days; one scalp numbness lasted 2.5 months.
5. BBB disruption, edema, swelling, hemorrhage or stroke: There is a potential risk of hemorrhage during ExAblate procedure

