8. Risk of cavitation - There is a risk of cavitation in the tissue at the focal point. Cavitation is the collapse of rapidly developed gas bubbles at the focal point due an extreme intensity of ultrasound excitation. This rapid collapse could cause high pressure, shock waves, and high temperatures. However, we believe that through proper system design and careful selection of system operation envelope, there is a very minimal risk that cavitation could occur during a treatment, even in the event of user error. We have developed an automated treatment planner that takes as its input the targeted ablation area depth in tissue, focal volume and tissue absorption, and based on pre-set safe operating limits selects sonication parameters that will keep the intensity of ultrasound excitation well below the intensity levels that could cause cavitation.

9. Risk related to sonication pathway - There is the risk that the tissue along the path to the target (scalp, skull, dura, brain, etc) could become heated to the point where tissue-damage might occur which could result in significant neurological damage or even death. This heating could be caused by direct improper treatment targeting, irregularities on the skin surface (e.g.: scars), treatment of a volume of tissue too close to the skin or bone, energy absorption by the bone, or the conduction of sufficient heat to cause a burn. The heating in the energy pass zone is always monitored and an additional cooling time can be administered when elevated temperatures are detected. Below are some possible risks related to the sonication pathway through different tissues in the head:.

- a. **Skin burn** is a potential risk due to improper acoustic coupling. There have been no cases of skin burn in all ExAblate transcranial treatments to date. The treatment set-up process includes filling the gap between the ultrasound transducer and the skull with a water-filled membrane to provide acoustic coupling. There is a possibility of small air bubbles remaining attached to the skin. These could cause a small focal hot spot and cause local pain or a burn to the scalp. The active cooling mechanism unique to this system is designed to reduce the risk of skin burns and

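### Section 6.1.7's statements on skin burns and on how quickly side effects resolve do not match the pilot data in the protocol's own Table 2

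*Protocol*

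**What the plan says.** Protocol Section 6 opens its list of risks with a link to consent: "The potential risks described below will be explained to the subject in the informed consent process".

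- **Section 6.1.7, item 9a (skin burn).** It says that skin burn "is a potential risk due to improper acoustic coupling", then reports past experience: "There have been no cases of skin burn in all ExAblate transcranial treatments to date".
- **Section 6.1.7, item 3 (light-headedness, dizziness, unsteadiness, nausea or vomiting).** Citing current data, it says "these events should be transient and resolve within a day or so".
- **Section 6.1.7, item 4 (numbness, tingling, twitch, paresthesia).** It says these are generally gone within minutes to a day and names two exceptions: "One paresthesia lasted for 4 days; one scalp numbness lasted 2.5 months".
- **Section 6.1.4 (head frame).** It describes how the frame's design limits skin events at the metal tips. It mentions no observed burn.

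Section 1.4.2.1.2.4 reports the ET-001 pilot: "Fifteen subjects were enrolled and treated at one site and the study report was recently completed". Its Table 2 covers device- and procedure-related events and includes, in the Significant class, the row "Burn – pin site | 1 | 1 | 0 | 2" (mild, moderate, severe, total). The text below the table says 61 of 82 events resolved within two weeks and 14 took longer, while "7 events (9%) were reported as ongoing".

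**The concern.** Item 9a is a statement of fact with no limit on type or site of burn, and a table in the same protocol contradicts it. The durations in items 3 and 4 are also presented as experience to date, yet about a quarter of the pilot events outlasted two weeks and some had not ended.

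These sentences are the source text for what subjects are told about an ablative brain procedure. A subject weighing a lasting sensory or balance effect, or a burn at the frame pins, would get a more favourable account from Section 6.1.7 than the sponsor's pilot supports. The text also carries forward: the risk analysis in the long-term follow-up protocol (ET002-LTF) adds no new risks and relies on those described in the original treatment protocol.

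**Working it through.** **1. Reproduce the plan's totals (Table 2 and the text below it).**

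- Non-significant: 45 + 14 = 59. Significant: 16 + 5 = 21. Incidental: 1 + 1 = 2. Total: 59 + 21 + 2 = 82, as stated.
- Within two weeks: 61/82 = 74.4%. Later: 14/82 = 17.1%. Ongoing: 7/82 = 8.5%. These match the stated 74%, 17% and 9%, and 61 + 14 + 7 = 82.
- One loose end: the text says the 14 leaves out one sinusitis case, yet the three groups already fill all 82 events. The late count could therefore be off by one.

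**2. Burns.** Item 9a gives 0. Table 2 gives 2 events. The lead-in to Table 2 speaks of numbers of patients, but the column header counts events, so the two burns may be in one or two subjects. Exact (Clopper-Pearson) 95% intervals:

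| Subjects with a burn | Incidence | 95% CI |
|---|---|---|
| 1 of 15 | 6.7% | 0.2% to 31.9% |
| 2 of 15 | 13.3% | 1.7% to 40.5% |

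Section 1.4.2.1.2 puts total transcranial thalamotomy experience above 50 subjects. Taking 50, and assuming no other burn, the figure is 1/50 to 2/50, or 2% to 4%. On any of these readings it is not zero.

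**3. Events beyond two weeks.** 82 − 61 = 21, which equals 14 + 7. As a share, 21/82 = 25.6%.

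**4. Make-up of the Significant class.**

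- Sensory: appendage paresthesia 2 + facial 5 + scalp 4 + scalp hypesthesia 1 + pin-site numbness 1 = 13.
- Balance: 4 (2 mild, 2 moderate).
- Other: fatigue 1 + pin-site infection 1 + pin-site burn 2 = 4.
- 13 + 4 + 4 = 21. Balance and sensory together: 17/21 = 81%.

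**5. What follows from arithmetic alone.** Assigning Table 2 rows to items 3 and 4 is my own reading.

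- Item 3 types: balance 7 + 4, emesis 2, nausea 6, light-headedness 8, ataxia 1 = 28.
- Item 4 types: 13 Significant sensory, 9 non-significant sensory (appendage numbness 1, appendage paresthesia 3, facial paresthesia 5), twitch 1 = 23.
- All others: 82 − 28 − 23 = 31.
- Same-day resolution is given as 49%: 0.49 × 82 ≈ 40, leaving 42. Even if all 31 other events were among those 42, at least 42 − 31 = 11 item 3 or item 4 events did not resolve the same day.
- The same bound does not place any of them beyond two weeks, because 31 exceeds 21. That step needs the inference in step 6.

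**6. What follows if the late events are the Significant events.** The counts match (21 and 21). Section 6.2 describes non-significant effects as normally resolving within 1 to 14 days and significant ones as having no defined resolution time. If the two sets coincide:

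- 13 sensory events lasted beyond two weeks, against one such case named in item 4 (the 2.5-month numbness);
- 4 balance events did so, against about a day in item 3;
- at least 7 − 4 = 3 of the 7 ongoing events were balance or sensory.

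**The case against.** **Different burns.** Item 9a sits under sonication-pathway risks and concerns acoustic coupling, while the pilot burns were at the pins. The protocol does separate the two: item 1 of Section 6.1.7 speaks of skin away from the pin sites, and Section 6.1.4 covers the metal tips. This is a fair defence of what may have been meant. But the sentence covers all treatments without qualification, and on the narrow reading the pin-site burns appear nowhere in Section 6.

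**Duration is hedged.** Item 4 says generally and gives two exceptions. Item 10 says the period of surrounding inflammation cannot be predicted and mentions two to three weeks. Light-headedness, nausea and vomiting are all in the Non-significant class; of the item 3 effects only balance appears among the Significant events. All of this stands. It limits the point to observed frequency and duration.

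**The 21 = 21 match is inference.** No row of Table 2 gives a resolution time. Section 6.2 also classifies by medical severity and treatment needed, so an infection or burn could be Significant without lasting. This stands too.

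**Stronger readings that the documents do not support.**

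- *A reader might infer that the consent form understates risk.* The form was not available for review. Section 6 shows only that these risks are to be explained.
- *A reader might infer that the risk section treats burns as no risk.* Item 9a calls skin burn a potential risk, Section 6.2 lists burns in both classes, and item 10 names permanent deficit. The zero describes past experience only.
- *A reader might infer that judgements on unanticipated adverse device effects are compromised.* Section 6.6 tests against the whole investigational plan, and Table 2 is part of it.

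**Conclusion.** The point holds as a factual inconsistency in safety text that feeds consent.

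- **Burns:** the contradiction is on the face of the protocol. The text says none; the pilot had 2 events, in 1 or 2 of 15 subjects (6.7% or 13.3%, with wide intervals). Quoting 13.3% alone would assume two separate subjects.
- **Duration:** 21 of 82 pilot events (26%) outlasted two weeks and 7 were ongoing. The wording of items 3 and 4 fits poorly with that and with a Significant class that is 17/21 balance or sensory. At least 11 events of the item 3 or item 4 type did not resolve the same day, given the rounded 49% and my assignment of rows. That balance and sensory events account for most of the late ones is strongly implied by the matching counts and the Section 6.2 definitions, but it is not shown row by row.

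It should be corrected. It does not affect the efficacy analysis, and it does not show that subjects were misinformed.

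**What to change.** Reconcile Sections 6.1.4 and 6.1.7 with Table 2:

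1. In item 9a, limit the sentence to scalp burns in the sonication path if that is what is meant; otherwise remove it.
2. In Section 6.1.4, report the two pin-site burns (one mild, one moderate) and state whether they were in one or two subjects.
3. In items 3 and 4, replace the duration wording with the ET-001 counts and the observed durations by event type, including ongoing events. The sponsor holds the resolution data, so this also settles whether the 21 late events are the 21 Significant ones and where the sinusitis case belongs.
4. Check that the consent form carries the same figures.

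The cost is protocol wording, any consent wording found not to agree, one tabulation of existing pilot data, and a slightly less favourable stated risk profile. No design, sample size or analysis changes.

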6.2 Anticipated Treatment Side Effects from ExAblate

All adverse events will be reported in the Case Report Forms (CRFs) and analyzed for their relationship to the treatment device, the procedure, and disease progression. Based on previous treatment experience, the following anticipated side effects have been identified as possible treatment related complications of ExAblate treatment. These can be classified into Non-significant and Significant Anticipated Treatment Side Effects based on their medical severity, additional treatment required, and long-term consequences for the subject.

Non-significant Anticipated Treatment Side Effects of ExAblate treatment are those that normally resolve without sequelae within 1-14 days of the treatment:

- minor pain from subject positioning or system interface (i.e. back pain, soreness in neck).
- transient fever: oral temperature $>100.4^{\circ}\text{F}/38^{\circ}\text{C}$, lasting less than 24 hours
- minor (1° or 2°) skin burns less than 2 cm in diameter
- bruising of the skin along the treatment path
- increase in edema surrounding the treatment area as shown on MRI.
- Headache
- Dizziness, nausea or vomiting

Significant Anticipated Treatment Side Effects of ExAblate are those which may require medical treatment, may have sequelae, and for which time of resolution is not defined. The following side effects are thought to be improbable but their relative risk remains to be defined:

Scalp in the sonication pathway:

- skin burns ($>2^{\circ}$) with ulceration of the skin
- scar formation
- Loss of sensation
- atrophy

Bone in the sonication pathway:

- bone necrosis

Dura, venous sinuses, and cortical veins

- subdural bleeding
- vein thrombosis
- Cortex
- seizures
- symptoms from disturbances of eloquent cortical areas (motor, sensory, auditory, visual, speech)

Other brain tissue

- necrosis of normal tissue due to incorrect targeting
- thermal damage to adjacent functional brain tissue (e.g.: optical tract)
- bleeding in the treated area
- cerebral infarction
- neurological deficits
- moderate or severe increase in cerebral edema as shown by MRI scans

- symptomatic increase of intracranial pressure
- death

Cerebral arteries

- bleeding
- coagulation thrombosis
- vasospasm
- death

The experience of Significant Anticipated Treatment Side Effects in ExAblate treatment in the breast and uterus have been less than 5% as shown in prior clinical experience. In brain treatments there is limited prior experience with the ExAblate Transcranial system and the probability of an adverse effect is unknown. It is the purpose of this study to gain experience that will allow us to evaluate the safety of ExAblate Transcranial system of TDPD (See also **Section-6.1.7.d**).

